#### **8.3.4 Removal of Subjects from Therapy or Assessments**

Subjects may stop study medication for any of the following reasons:

- Subject request.
- Use of non-permitted concurrent therapy.
- Noncompliance with the study medication (see Section 8.5.9).
- Noncompliance with the study procedures (see Section 8.5.9 and Section 8.6).
- Lost to follow-up.
- Occurrence of AEs not compatible with the continuation of subject participation in the study, in the investigator's opinion. This also includes any clinically significant laboratory results, ECGs and vital signs.
- Investigator request.
- Sponsor request.
- Treatment failure deemed by the investigator as lack of improvement or worsening of the disease symptoms or occurrence of intolerable AEs.

Treatment with GLPG0634 will be discontinued and the subject withdrawn from this study for:

- Serious infections (those requiring parenteral antimicrobial therapy or hospitalization).
- Any opportunistic infections.
- Complicated herpes zoster infection (multi-dermatomal, disseminated, ophthalmic or CNS involvement).
- Two sequential total white cell counts  $<2000$  cells/mm^3 (SI:  $<2.0 \times 10^9$  cells/L).
- Two sequential neutrophil counts  $<1000$  neutrophils/mm^3 (SI:  $<1.0 \times 10^9$  cells/L).
- Two sequential lymphocyte counts  $<750$  lymphocytes/mm^3 (SI:  $<0.75 \times 10^9$  cells/L).
- Two sequential hemoglobin  $<8.0$  g/dL (SI:  $<80$  g/L).
- Two sequential platelet counts  $<75,000$  platelets/mm^3 (SI:  $<75.0 \times 10^9$  cells/L).
- Two sequential AST or ALT elevations  $>3$  times the upper limit of normal with at least one total Bilirubin value  $>2$  times the upper limit of normal.
- Two sequential AST or ALT elevations  $>3$  times the upper limit of normal accompanied by symptoms consistent with hepatic injury.

- 
- Two sequential AST or ALT elevations >3 times the upper limit of normal accompanied by elevated INR.
  - Two sequential AST or ALT elevations >5 times the upper limit of normal, regardless of total Bilirubin or accompanying symptoms.
  - Two sequential increases in serum creatinine >50% over the average of screening and baseline values.
  - Two sequential decreases from the baseline of inhibin B by 50% or testosterone by 50% with concurrent increases in FSH or LH respectively.

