## **3.2. ANALYSIS PERIODS FOR NON-VISIT DATA**

These analysis periods are to be used for allocation of adverse events and concomitant medications into periods.

Analysis period	Period start date	Period end date
Screening	Date of signing the initial ICF.	First study drug administration date – 1 day.
First 12 weeks	First study drug administration date.	Date of the W12 visit.
Second 12 weeks	Date of the W12 visit + 1 day.	Max ( trial termination date ; date of last dose + 30 days ).
Full 24 weeks	First study drug administration date.	Max ( trial termination date ; date of last dose + 30 days ).

The trial termination date is the date of last contact with the subject, as recorded in the eCRF.

Note that the last analysis period in case of early termination will always be ended by: *Maximum ( trial termination date ; date of last dose + 30 days)*. In case the subject rolls over to DARWIN3, the trial termination date will be used (no 30 days will be added since that would be during DARWIN3).

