### **4.4.3. Handling of missing values and early dropouts in the efficacy analyses during the first study period (up to Week 12)**

This is for the “efficacy chapter 2” analysis.

For binary data (e.g., ACR20), two different imputations will be done for missing visits as well as early dropouts: non-responder imputation (NRI) and LOCF, up to and including Week 12. The NRI imputation will be primary, and LOCF will be secondary.

For other data (ordinal or continuous), missing visits as well as early dropouts will be imputed using the last observation carried forward (LOCF) algorithm, up to and including Week 12.

Definitions of the imputation methods:

- LOCF (all types of parameters, from binary to continuous): to impute a missing value, the last preceding nonmissing value will be used (which could even be a baseline value).
- NRI (binary response parameters only): to impute a missing response, the subject will be assumed to be a non-responder.

For all parameters, an observed-case analysis will also be performed (i.e., without any imputation). The observed-case analysis will serve as a sensitivity analysis (to ascertain the impact of early dropouts on the results) and will basically be limited to:

- ACR20/50/70/N: descriptive at W12+W24 and inferential at W12
- EULAR remission: descriptive at W12+W24
- SDAI/CDAI: descriptive at BSL+W12+W24
- DAS28: descriptive at BSL+W12+W24 and inferential at W12
- All ACR components (VAS, joint counts, CRP, HAQ-DI): descriptive at BSL+W12+W24
- QoL (FACIT,SF-36): descriptive at BSL+W12+W24.

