#### The time to ACR20 response

= (date of first time ACR20 response is reached) – (date of first medication intake) + 1 day, if the subject achieved ACR20 response during the initial 12 weeks treatment period, or  
= MIN (date of the Week 12 visit , date of trial termination) – (date of first medication intake) + 1 day, in case the subject did not achieve ACR20 response at any time during the initial 12 weeks treatment period.

Next to this, the visit during which the ACR20 response was first recorded will be analyzed as well:

- Week 1
- Week 2
- Week 4
- Week 8
- Week 12
- Never (i.e., subject did not achieve ACR20 response during the initial 12 weeks of treatment).

The time to ACR50 response and the time to ACR70 response are defined in the same way.

Note that the study period 2 cannot be used for the time-to-event derivation, because of the predefined potential treatment shifts at Week 12.

Note that if for a specific visit both the regular CRP as well as the high-sensitive CRP are available, the high-sensitive CRP will be used for the derivation of the percentage change from baseline and also for the ACR20/50/70/N.

Note that the percentage change from baseline remains missing if the baseline value itself equals zero.

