**Table 14.2.1.1.15: Time to ACR20 response: Summary with overall p-value and pairwise comparisons versus placebo**

Descriptive statistics per treatment group.

Between-group comparison (overall and all pairwise comparisons versus placebo)

P-values are generated from a Cox proportional hazards regression model. Factors in the model are: treatment, region, and previous use of biologics.

The table will present:

- Per group: N (number of events, number of censored, number in total), mean (SE), median, quartiles.

- Overall type-III p-values for treatment, region and previous use of biologics.
- Per group: p-value for pairwise comparison versus the placebo group. These p-values will be corrected for multiplicity according to Hommel's closed-testing method as implemented in SAS PROC MULTTEST. The uncorrected p-values will also be presented.

A frequency table of the time-to-event in categories (Week 1, Week 2, Week 4, Week 8, Week 12, never) will also be presented.

The "raw" SAS PROC output must be provided in a statistical appendix listing.

Population: ITT.

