**Figure 14.2.1.1.6: Time to ACR20 response: Kaplan-Meier plot**

Ascending Kaplan-Meier plot per treatment group.

Population: ITT.

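### Censoring early leavers without response at trial termination makes the ascending Kaplan-Meier time-to-response curves overstate the share who respond by Week 12; one common end time for all never-responders fixes this cheaply

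*SAP*

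**What the plan says.** SAP 8.1.1 gives a subject without ACR20 response in the first 12 weeks an end time of "MIN (date of the Week 12 visit , date of trial termination", counted from first intake. ACR50 and ACR70 are handled the same way. SAP 3.2 defines the second date: "The trial termination date is the date of last contact with the subject, as recorded in the eCRF".

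Table 14.2.1.1.15 reports "N (number of events, number of censored, number in total), mean (SE), median, quartiles". A never-responder is thus a censored subject. Tables 14.2.1.1.18 and 14.2.1.1.21 repeat this for ACR50 and ACR70. The test in the same table is a Cox model: "P-values are generated from a Cox proportional hazards regression model". Figures 14.2.1.1.6 to 14.2.1.1.8 are each specified as "Ascending Kaplan-Meier plot per treatment group".

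Elsewhere the same early leaver counts as not responding. Under NRI, the primary imputation for binary data (SAP 4.4.3), the rule is "to impute a missing response, the subject will be assumed to be a non-responder". The time-to-response table adds: "A frequency table of the time-to-event in categories (Week 1, Week 2, Week 4, Week 8, Week 12, never) will also be presented". A leaver without response falls in the last of these categories.

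The SAP names no competing-event method and no sensitivity analysis for this censoring.

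**The concern.** An ascending Kaplan-Meier curve estimates the share who would respond by a given day if nobody left, assuming leavers would have responded later at the rate of those who stayed. In this trial the early discontinuation visit is the last efficacy assessment for a leaver (Protocol 8.7.1.1.1), so no later response can be recorded. The assumption is also doubtful on its face, because Protocol 8.3.4 lists among the reasons to stop "Treatment failure deemed by the investigator as lack of improvement or worsening of the disease symptoms or occurrence of intolerable AEs".

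A reader of a dose-finding report will take the height of the curve as the share of the arm that has responded. Read that way it is too high wherever subjects leave without response. Medians and quartiles, if taken from the same Kaplan-Meier estimate, may come too early.

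**Working it through.** **The plan's own figures.** The plan states no cumulative response rate and no dropout rate. Its only related figures are the powers in Protocol 8.8.2. With 85 per arm and two-sided alpha 0.05/6 = 0.0083, the chi-square formula gives 0.898 (48% vs 20%), 0.913 (70% vs 40%), 0.809 (45% vs 20%) and 0.784 (66% vs 40%), close to the stated 90/90/80/80%. Those response rates set the scale below.

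**Inputs.** From the documents: 85 per arm; efficacy visits at Weeks 1, 2, 4, 8 and 12. Assumed: cumulative first response F without dropout at those visits,
- 40% (placebo-like): 0.06, 0.12, 0.22, 0.33, 0.40
- 60%: 0.15, 0.25, 0.40, 0.52, 0.60
- 75%: 0.18, 0.32, 0.52, 0.66, 0.75
- 80%: 0.20, 0.36, 0.57, 0.72, 0.80

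and a constant weekly dropout hazard λ among subjects who have not yet responded.

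**Formulas.** With visits at their nominal times t_i:
- end of the ascending Kaplan-Meier curve = F_5
- proportion seen to respond = Σ (F_i − F_{i−1}) e^{−λ t_i}
- proportion leaving without response = Σ (1 − F_{i−1})(e^{−λ t_{i−1}} − e^{−λ t_i})

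**Worked case: 60% curve, 8% leaving without response.** λ = 0.01104 per week gives 0.0110 + 0.0092 + 0.0160 + 0.0248 + 0.0190 = 0.080 leaving. The proportion responding is 0.15×0.9890 + 0.10×0.9782 + 0.15×0.9568 + 0.12×0.9155 + 0.08×0.8759 = 0.1484 + 0.0978 + 0.1435 + 0.1099 + 0.0701 = 0.570. The curve ends at 0.600, so it is 3.0 points too high. With SE = √(0.570×0.430/85) = 0.0537, that is 0.57 SE.

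**Excess in points, by share of the arm leaving without response:**

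| Curve | 5% | 8% | 10% |
|---|---|---|---|
| 40% | 1.2 | 2.0 | 2.5 |
| 60% | 1.9 | 3.0 | 3.8 |
| 75% | 2.7 | 4.3 | 5.5 |
| 80% | 3.0 | 4.8 | 6.0 |

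At 3% leaving, the excess stays below half an SE on every curve. If last contact is a Follow-up visit about 8.5 days after the early discontinuation visit, the excess falls by about one sixth (2.5 to 4.1 points on the active curves at 8%).

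**Median.** At 5% the median visit does not move on any active curve. At 8% on the 60% curve, the Week 8 value drops from 0.52 to 0.1484 + 0.0978 + 0.1435 + 0.1099 = 0.4996, just under one half. A shift is therefore possible but not general.

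**Active against placebo.** The table fixes the same share of each arm leaving. Responders are no longer at risk of leaving without response, so an equal share implies a higher hazard in the better-responding arm: at 8%, 1.25, 1.5 and 1.6 times the placebo hazard for the 60%, 75% and 80% curves. With equal hazards instead (8% leaving on placebo), the excess is 2.5 to 3.0 points active against 2.0 placebo. With the placebo hazard 1.5 times the active hazard, it is 1.7 to 2.0 active against 2.0 placebo.

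A second set used the protocol's rates directly, a 10% chance of leaving by Week 12 for a subject not responding, and fast to linear onset. With equal hazards, the excess is 1.6 to 2.7 points at 48% and 0.7 to 1.1 at 20%; it is 2.3 to 3.9 at 70% and 1.3 to 2.2 at 40%. With twice the active hazard on placebo and fast onset, the order holds for 48% vs 20% (1.6 against 1.3) but reverses for 70% vs 40% (2.3 against 2.6).

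**Week 12 completers.** Early leavers are not the whole problem. A completer without response is censored on the day of the Week 12 visit, while others may respond at visits up to 4 days later (window ±2 days). Assume no dropout and Week 12 visits spread evenly over those 5 days, and let h be the conditional response probability at Week 12. The curve then ends at 1 − (1 − F_4)(1 − h/5)(1 − h/4)(1 − h/3)(1 − h/2)(1 − h). For the 60% curve, h = 0.08/0.48 = 1/6 and the end is 1 − 0.48×0.6683 = 0.679 instead of 0.600. The 40%, 75% and 80% curves end at 47.7, 82.5 and 86.4%. A remedy limited to discontinued subjects would leave this in place.

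**The case against.** The case for leaving the plan alone has real content. Censoring at departure is standard for a cause-specific hazard, so the Cox comparisons stand. The primary endpoint, ACR20 at Week 12 by NRI, does not use this derivation, and the level of response is tabulated and plotted with NRI at every visit. The Never category lets a reader of the table recover events/N. All dropout inputs above are assumed, and with little dropout the effect is small.

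NRI also answers a different question. It scores response at a given visit, whereas this endpoint is first response at any visit. A Week 4 responder who then leaves is an event here but a Week 12 non-responder under NRI. The mismatch is thus a departure from the plan's handling of dropouts, not a flat contradiction.

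A reader might also infer that Table 14.2.1.1.15 reports two different Week 12 response rates. It does not: it lists no Kaplan-Meier rate at Week 12, and its event count agrees with its Never row.

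What remains is that the figures, read alone, show a level that no count in the trial supports.

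**Conclusion.** The point holds as a cheap improvement to secondary, descriptive outputs. The curves are biased upward as a measure of the share responding, in every arm where subjects leave without response before the last events. The size is about 1 to 6 points for an assumed 5 to 10% leaving, over ever-response rates of 40 to 80%. Medians and quartiles may be affected.

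Two stronger readings are tempting. One is that the bias favours active arms over placebo. That requires similar dropout hazards among non-responders; the documents give no dropout by arm, and higher placebo dropout removes or reverses the difference. Stopping for lack of improvement could well be commoner on placebo. The other is that preliminary phase III dose selection is distorted. Protocol 8.8.1.5 and SAP 6.2 tie that selection to the Week 12 interim, where time to response is not among the listed efficacy outputs, and none of these tables or figures is marked for it.

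**What to change.** In SAP 8.1.1, for the curves, medians and quartiles of time to ACR20/50/70 response, use one of two rules:

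- Give all subjects without response by Week 12, early leavers and Week 12 completers alike, one common censoring time at or after the end of the Week 12 analysis window (Day 98 in SAP 3.3). No one is then censored before the last event, so the Kaplan-Meier curve ends at events/N.
- Alternatively, use nominal visit times and plot the cumulative incidence of first response, with discontinuation before response as a competing event.

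Either way each curve ends at one minus the Never rate. Keep the present censoring as a labelled sensitivity analysis. The Cox comparisons can stay, described as cause-specific.

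The cost is a changed derivation and a re-run of three figures (14.2.1.1.6 to 14.2.1.1.8) and three tables (14.2.1.1.15, .18 and .21), with no new data. The downside is that reported cumulative response will be a few points lower and arms with more withdrawals will look slightly less favourable.

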### **8.1.2. Tables over the whole 24 weeks period**

Tables will present Weeks 1-2-4-8-12-16-20-24, unless specified otherwise. Tables will present the imputed 7 treatment groups, as mentioned in section 2.1.1.

#### **Table 14.2.1.1.1: ACR20: Summary with overall p-value and pairwise comparisons versus placebo**

Logistic regression model at each time point, modeling the responders. Factors in the model are: treatment, region, and previous use of biologics.

Per time point, the table will present:

- Overall type-III p-value for all explanatory factors in the model.
- Per group: number and percentage of responders, difference in percentage responders versus the placebo group (GLPG0634 minus placebo), together with a 95% confidence interval of this difference (as provided by SAS PROC FREQ).
- Per group: p-value for pairwise comparison versus the placebo group, derived from contrasts within the overall regression model. These p-values will be presented both as uncorrected p-values as well as corrected for multiplicity according to Hommel's closed-testing method (SAS PROC MULTTEST).

The "raw" SAS PROC output must be provided in a statistical appendix listing.

The table will show:

- NRI in ITT and in per-protocol
- LOCF in ITT and in per-protocol
- observed-case in ITT (descriptive at Week 12 + 24; inferential statistics at Week 12 only).

Table to be created for the Week 12 interim analysis as well, cut off at Week 12. ITT only.

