### **8.5.4 Method of Assigning Subjects to Treatment Groups**

Subjects will be randomly allocated to treatment according to a pre-specified randomization scheme prepared by an independent statistician within [REDACTED]. Upon qualification for the study, subjects ([REDACTED]) will be randomized using a computerized IXRS system ([REDACTED], Belgium) to placebo or one of 6 dosing regimens (3 dose levels of GLPG0634 administered either once or twice daily) in a 1:1:1:1:1:1 ratio, stratified by region and previous use of a biological DMARD during a single clinical study setting.

[REDACTED]

A total of 595 subjects will be randomized (N=85 for each treatment group).

For each subject at each visit, the clinic will contact the IXRS system and for the appropriate kit number to be dispensed. The kit will contain the relevant study medication for the period until the next visit.

At Week 12, subjects on placebo who have not achieved a 20% improvement in SJC66 and TJC68 will be re-randomized (automatically via IXRS) to treatment to receive GLPG0634 100 mg q.d. or 50 mg b.i.d. doses in a blinded fashion, subjects on 50 mg q.d. who have not achieved a 20% improvement in SJC66 and TJC68 will be assigned to 100 mg q.d., and

CONFIDENTIAL

---

subjects on 25 mg b.i.d. who have not achieved a 20% improvement in SJC66 and TJC68 will be assigned to 50 mg b.i.d. All will continue the study until Week 24. Subjects in the other groups will maintain their randomized treatment until Week 24.

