## **8.8.2 Determination of Sample Size**

The sample size calculation is based on the expected ACR20 response rates at Week 12.

Assuming:

- 7 treatment arms with an equal 1:1:1:1:1:1:1 group allocation (n=85 for each dose group, total N=595).
- $\alpha=5\%/6=0.83\%$  per comparison versus placebo.
- a 20%-40% placebo ACR20 response at Week 12.

Then the study has 90% power to detect a minimum 28% (=48% - 20%) to 30% (=70% - 40%) treatment difference versus placebo, depending on the placebo response rate. This is considered clinically meaningful.

The study also has 80% power to detect a 25% (= 45% - 20%) to 26% (= 66% - 40%) treatment difference versus placebo, depending on the placebo response rate.

Calculations were performed using a chi-square approach in nQuery 7.0.

Note that the type-I error rate was Bonferroni-adjusted for the 6 comparisons versus the placebo group, and no further correction of the type-I error rate is required for the Week 12 interim analysis because it matches the primary efficacy analysis (ACR20 at Week 12).

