## 1.2. STUDY DESIGN

This is a multicenter, phase IIb, double-blind, placebo-controlled add on study in subjects with moderately to severely active RA who have an inadequate response to MTX. A total of 595 subjects will be randomized to one of 6 dose regimens of GLPG0634 or to placebo, on top of their stable dose of MTX. Treatment duration will be 24 weeks. At Week 12, subjects on placebo who have not achieved a 20% improvement in swollen joint count (SJC66) and tender joint count (TJC68) will be re-randomized (automatically via interactive voice/web response [IXRS]) to treatment to receive GLPG0634 100 mg q.d. or 50 mg b.i.d. doses in a blinded fashion, subjects on 50 mg q.d. who have not achieved a 20% improvement in SJC66 and TJC68 will be assigned to 100 mg q.d. and subjects on 25 mg b.i.d. who have not achieved a 20% improvement in SJC66 and TJC68 will be assigned to 50 mg b.i.d. All will continue the study until Week 24. Subjects in the other treatment groups will maintain their randomized treatment until Week 24.

Upon qualification for the study, subjects will be randomized to placebo or one of 6 dosing regimens in a 1:1:1:1:1:1 ratio (N=85 for each treatment group; total N=595), stratified by geographic region and previous use of a biological DMARD during a single clinical study setting.

[figure not shown]
Subjects participating in the study will be requested to attend a maximum of 11 visits throughout the study: Screening visit (up to 28 days before Baseline visit), Baseline visit, Week 1 visit, Week 2 visit, Week 4 visit, Week 8 visit, Week 12 visit, Week 16 visit, Week 20 visit, Week 24 visit (and potentially a follow-up visit). At completion of the 24-week

treatment period, subjects will be offered the option to enter a Long Term Follow-up study (GLPG0634-CL-205). For the subjects not entering the GLPG0634-CL-205, an additional final Follow-up visit will be scheduled 7 to 10 days after end of study treatment.

Consequently, each subject will remain in the study for a maximum of 29 weeks (from Screening visit to Follow-up visit).

Data from the Long Term Follow-up study 205 will be presented in a separate analysis, and is not part of this SAP.

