**Note that the primary endpoint of the study is the ACR20 at Week 12 in the ITT population, using NRI imputation.**

The ACR-N is derived using the following formula:

$$\text{ACR-N} = \text{MIN} [ \% \text{ improvement in TJC68, } \% \text{ improvement in SJC66, MED } \% \text{ improvement in (patient's global assessment, physician's global assessment, patient's assessment of pain, HAQ-DI, CRP) } ]$$

So this is taking the smallest of the percentage increases in SJC66, TJC68, and the third of the remaining 5 parameters. In case the ACR-N is negative (i.e., the subject actually worsens instead of improves), then the ACR-N is replaced by a 0. The ACR-N is therefore a number between 0 and 100.

The ACR-N represents the percentage NN% according to which the subjects would have been an "ACRNN" responder.

(See further sections on how to derive these components.)

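### The ACR20 difference and its 95% CI are raw PROC FREQ values with no strata named, though randomisation and the adjacent p-value use region and prior biologics; they should be adjusted and labelled per-comparison

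*SAP*

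**What the plan says.** SAP section 8.1.1 fixes the primary analysis: "Note that the primary endpoint of the study is the ACR20 at Week 12 in the ITT population, using NRI imputation".

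Table 14.2.1.1.1 (SAP 8.1.2) is the main table for it. It gives the number and percentage of responders per arm and the difference from placebo "together with a 95% confidence interval of this difference (as provided by SAS PROC FREQ". It names no strata, interval type or multiplicity rule for that interval. The table specification lists no odds ratio or adjusted difference.

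The p-values in the same table come from contrasts in a logistic regression: "Factors in the model are: treatment, region, and previous use of biologics". On multiplicity the table says: "These p-values will be presented both as uncorrected p-values as well as corrected for multiplicity", the correction being Hommel's.

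Randomisation uses the same two factors. Protocol 8.5.4 has allocation "stratified by region and previous use of a biological DMARD during a single clinical study setting", and SAP 1.2 agrees.

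The SAP treats continuous endpoints differently. Table 14.2.1.3.4 (SDAI and CDAI) takes the difference in LS-means and its 95% CI from a model that contains region and previous biologics.

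**The concern.** The effect estimate and its interval appear to come from one analysis and the test from another. The allocation is balanced on region and prior biologics, and the test uses that balance. The interval, as written, does not. When response differs by region, an interval that ignores region counts between-region variation as noise and is wider than it needs to be. The raw difference is also not the quantity the logistic contrast tests.

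A second, smaller gap concerns reading the table. Six 95% intervals against one placebo arm sit beside two sets of p-values. Neither document says which set the intervals pair with, or which result governs when they differ. The table is also produced for the Week 12 interim analysis, which is meant to inform preliminary phase III dose selection.

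**Working it through.** **1. The plan's own figures.** Protocol 8.8.2 assumes "7 treatment arms with an equal 1:1:1:1:1:1:1 group allocation (n=85 for each dose group, total N=595", alpha = 0.05/6 = 0.00833 per comparison and a 20 to 40% placebo response. A two-sided chi-square calculation without continuity correction gives:

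| Placebo v dose | Stated power | Recomputed |
|---|---|---|
| 20% v 48% | 90% | 89.8% |
| 40% v 70% | 90% | 91.3% |
| 20% v 45% | 80% | 80.9% |
| 40% v 66% | 80% | 78.4% |

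The plan does not state sidedness. Two-sided reproduces its figures.

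**2. Width of the planned interval.** Half-width = 1.96 × √[(pc(1−pc) + pt(1−pt))/85].
- 20% v 48%: 1.96 × √[(0.1600 + 0.2496)/85] = 13.6 points.
- 40% v 70%: 1.96 × √[(0.24 + 0.21)/85] = 14.3 points.

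**3. What adjustment for region gains.** The variance left within regions is p(1−p) − B, where B is the variance of the regional response rates. The SAP lists four regions (Listing 16.2.1.1). Assume that they are of equal size with rates evenly spaced over a span S, so the offsets from the mean are ±S/2 and ±S/6. Then B = (2·S²/4 + 2·S²/36)/4 = 5S²/36. At an overall rate of 50%, p(1−p) = 0.25 and the width ratio is √(1 − B/0.25).

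| Regional span S | B | Width ratio | Narrower by |
|---|---|---|---|
| 15 points | 0.0031 | 0.994 | 0.6% |
| 30 points | 0.0125 | 0.975 | 2.5% |
| 45 points | 0.0281 | 0.942 | 5.8% |

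Simulation gives about 0%, 2% and 6% at these spans, with the unstratified interval covering 96% at 45 points, so it is slightly conservative. In points, the gain runs from 0.02 × 13.6 = 0.3 to 0.06 × 14.3 = 0.9 on the half-width.

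**4. Interval against the uncorrected p-value.** This used 3,000 simulated trials per scenario with 85 per arm, assumed regional effects and 8% prior biologic use (assumed). The unstratified 95% interval and the adjusted, uncorrected p-value disagreed in 0.1 to 0.8% of comparisons.

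**5. Joint coverage of the six intervals.** The shared placebo arm gives correlation rho = Vc/(Vc + Vt), with V = p(1−p).
- Equal rates: rho = 0.5, joint coverage 79.3%.
- 20% v 48%: rho = 0.16/0.4096 = 0.39, coverage 77.3%.
- 40% v 70%: rho = 0.24/0.45 = 0.53, coverage 79.9%.

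Independence would give 0.95⁶ = 73.5%.

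**6. Interval against the Hommel-corrected p-value.** In the step 4 simulation, the share of trials in which the interval and the Hommel result disagree for at least one arm, nearly always an interval excluding 0 without Hommel significance, is:
- no true effect in any arm: about 19 to 21%;
- graded effects (+10/+20/+30 points on 40%, +10/+20/+28 on 20%): about 41 to 43%, or 9% of comparisons;
- all arms at the design effect: 3 to 4%.

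**7. A Bonferroni interval.** At 1 − 0.05/6 = 99.17% the multiplier is 2.638, and 2.638/1.96 = 1.35. Half-widths become 18.3 and 19.2 points. With all arms at the design effects, this interval disagrees with Hommel in at least one arm in about 21 to 24% of trials. The planned 95% interval does so in about 3 to 5%.

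**The case against.** The strongest reply is that nothing here changes the formal result. The primary test is the Hommel-corrected p-value, which controls type I error whatever interval is printed. The uncorrected p-value stands in the same table, and the 95% interval agrees with it in more than 99% of comparisons. The unstratified interval errs on the wide side. All of this stands, and it limits the point to precision and reporting.

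It is also fair that the lack of stratification is inferred. The SAP names no PROC FREQ option, and the table mocks are in a separate document. The natural reading is an unstratified interval, and if strata are intended the text should say so.

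A reader might go further in four ways that the documents do not support.
- **Joint coverage of 77 to 80% is a failure of the plan.** Neither document claims simultaneous coverage for these intervals.
- **The ACR20 interval decides the dose.** SAP 6.2 lists many efficacy and safety outputs for the interim and ties no rule to this interval.
- **Simple large-sample limits collapse when an arm has no responders.** That does not bear on Week 12 ACR20, where the plan assumes 20 to 40% response on placebo, and the SAP does not specify those limits.
- **The intervals should be widened to match the correction.** A Bonferroni interval does not match Hommel, which rejects more often, and step 7 shows that it disagrees more with the formal test at the design effects.

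**Conclusion.** The point holds as a modest one. The primary effect estimate and its interval are specified without the randomisation factors that the p-value uses, and the SAP already does better for its continuous endpoints. As written, the interval is about 2 to 6% too wide if regional response rates span 30 to 45 points, and the loss is negligible at 15 points or less. Those spans are assumptions, because the documents give no regional rates. The difference and interval are also not the estimate that the model tests.

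Nearly all visible disagreement between interval and corrected p-value comes from the multiplicity correction and hardly any from the missing strata. It calls for labelling and a stated order of precedence. Type I error control and the sample size are unaffected.

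**What to change.** In SAP Table 14.2.1.1.1:

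- Replace the PROC FREQ difference and interval with a difference and 95% CI adjusted for region and prior biologics. Two methods would serve: a standardised risk difference from the same logistic model, or a Mantel-Haenszel-weighted difference with stratified Newcombe limits. Name the method.
- Use the same method in the tables that repeat this layout: ACR50, ACR70, EULAR remission, SDAI and CDAI remission, and DAS28(CRP) remission with or without low disease activity.
- Label the six placebo comparisons as per-comparison 95% intervals that pair with the uncorrected p-value, and say that they are not simultaneous.
- State that the Hommel-corrected p-value governs the formal conclusion for each dose.
- Do not add a 99.17% interval.

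The cost is a few sentences in the SAP and minor programming. It needs no new data and no change in sample size.
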